1.2 Secondary Objectives

- Compare the distribution ^{18}F -DCFBC with multiparametric MRI and whole mount histopathology in patients undergoing prostatectomy
- Evaluate the distribution ^{18}F -DCFBC uptake in prostate cancer patients with biochemical relapse (site of recurrence unknown)
- Compare focal ^{18}F -DCFBC uptake with focal abnormalities identified on standard of care imaging
- Compare the uptake of ^{18}F -DCFBC in bone with respect to Na^{18}F PET/CT in patients with metastatic disease (the emerging gold standard, for detection of bony metastases).
- Evaluate the change over time in ^{18}F -DCFBC distribution in patients with known metastatic disease with clinical follow-up data 4-6 months post baseline ^{18}F -DCFBC PET/CT (e.g. understand the effect of androgen deprivation therapy (ADT) on ^{18}F -DCFBC uptake)

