2.3 Rationale

We propose to further expand upon initial clinical work with ^{18}F DCFBC and evaluate its usefulness in three different categories of prostate cancer- localized, metastatic and biochemical recurrence. In the case of localized disease ^{18}F DCFBC distribution will be compared with endorectal coil multiparametric MRI at 3T. In the case of potentially recurrent or metastatic disease ^{18}F DCFBC will be compared with CT, bone scan and/or Sodium Fluoride PET/CT bone scan. This study should offer insights into how and when ^{18}F DCFBC could be used in the clinical setting to direct proper management. Moreover, by monitoring ^{18}F DCFBC uptake in metastatic disease over time, one may better understand how useful this agent may be in monitoring responses to therapy.

Amendment C Addendum:

The agent has shown some preliminary promising results. In Arm 2, we have had patients with questionable uptake only near the bladder. We have noted that bladder activity may obscure possible prostate bed recurrence, so a recent amendment was approved for urinary catheterization with possible bladder irrigation. We have only been able to scan a limited

CC Protocol Number: 14-C-0140
Abbreviated Title: DCFBC in prostate cancer
Version date: 10/27/2015
CIP #: 9622

number of patients using this technique and have been able to locate areas suspicious for recurrence in some. Additional patients will help to determine if the technique is beneficial in visualization, potentially improving detection rates for early local recurrence. In Arm 3, we have noted a mixed response in tracer uptake for hormone sensitive patients, which contradicts what other PSMA research groups are reporting. They assert that uptake is always positive in patients on anti-androgen treatment. Our findings could be due to the heterogeneous evolution of lesions to castrate resistance, but currently our numbers are small. More patients to this arm will allow better characterization of the relationship between 18F DCFBC uptake and androgen deprivation therapy.

Amendment E Addendum:

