4 STUDY IMPLEMENTATION

4.1 Study Design

This is an open-label, 3-armed single-center pilot study. 110 evaluable subjects will be enrolled into the study (12 evaluable patients in arm 1; 78 evaluable patients in arm 2, and 20 evaluable patients in arm 3). An evaluable patient is defined as a patient who completes all required study procedures according to the assigned study arm. In order to allow for a small number of nonevaluable patients, the accrual ceiling will be set at 125.

Informed consent will be obtained prior to study enrollment. All subjects will undergo ^{18}F DCFBC injection and PET/CT imaging.

Patients in Arms 1 and 2 will undergo a single ^{18}F DCFBC PET/CT.

Patients in Arm 1 will have undergone a standard of care biopsy or clinically indicated prostatectomy. Specimens will be whole mounted on glass slides and regions of malignant tumor will be marked by the pathologist.

When possible, uptake of ^{18}F DCFBC depicted on PET/CT in Arms 2 and 3 will be validated with biopsy.

Patients in Arm 2 will be followed for clinical, imaging or pathologic data that may be obtained by their medical team within 12 months of imaging to determine if associations with ^{18}F DCFBC PET/CT can be seen.

CC Protocol Number: 14-C-0140
Abbreviated Title: DCFBC in prostate cancer
Version date: 10/27/2015
CIP #: 9622

Subjects in the metastatic disease arm (Arm 3) (as well as individuals who cross over into Arm 3) will undergo 2 separate ^{18}F DCFBC PET/CT imaging sessions, one at initial enrollment, and a second upon clinical follow-up (4-6 months after baseline ^{18}F DCFBC).

Patients in Arm 3 will also undergo a whole body Na^{18}F PET/CT scan within 3 weeks of each ^{18}F DCFBC to assess for potential early bone metastases. Changes in distribution of each radiotracer over the 4-6 month period will be compared with clinical data and imaging (obtained as standard of care) at that time. Each ^{18}F DCFBC PET/CT will be compared with the corresponding Na^{18}F PET/CT scan when obtained.

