14.2 Secondary Analysis

For patients with localized disease, the diagnostic accuracy of ^{18}F -DCFBC PET/CT will be compared with multiparametric MRI using the sector-based analysis. Patient-specific sensitivity and specificity will be estimated and differences in sensitivity and specificity between different modalities will be tested by the Wilcoxon signed-rank test. Change of ^{18}F -DCFBC uptake for patients with metastatic disease over time will be estimated by the linear mixed effect model where random intercept will be used to account for the intra-patient correlation of longitudinal ^{18}F -DCFBC uptake. In addition, in patients with metastatic prostate cancer to bone, the uptake of ^{18}F -DCFBC will be correlated with the uptake of the emerging gold standard, ^{18}F Sodium Fluoride PET/CT by the Spearman rank correlation.

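### The only method in section 14 that names NaF is a rank correlation of uptake, which cannot show how often DCFBC and NaF agree on bone sites

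*Combined protocol and SAP*

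**What the plan says.** - **Objective (1.2 Secondary Objectives).** Bone uptake of DCFBC is to be compared with NaF PET/CT in metastatic disease. NaF is described as "the emerging gold standard, for detection of bony metastases".
- **Design (4.1 Study Design).** Arm 3 patients have a NaF scan within 3 weeks of each DCFBC scan "to assess for potential early bone metastases". Each DCFBC "PET/CT will be compared with the corresponding" NaF scan, but no measure or method is given.
- **Analysis (14.2 Secondary Analysis).** The plan is that "in patients with metastatic prostate cancer to bone, the uptake of" DCFBC "will be correlated with the uptake of the emerging gold standard", namely "F Sodium Fluoride PET/CT by the Spearman rank correlation".
- **Site-level measures (14.1 and 14.3).** The concordance proportion and the interim PET-positive rate are both defined against conventional imaging. Neither section names NaF, and the term is not defined.
- **Rationale (2.3).** In recurrent or metastatic disease, "DCFBC will be compared with CT, bone scan and/or Sodium Fluoride PET/CT bone scan". No method is attached.

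**The concern.** The protocol treats NaF as the reference for finding bone disease, so the natural question in Arm 3 is how often the two tracers call the same bone sites positive, and in which direction they differ. A rank correlation answers another question: whether sites or patients with higher NaF uptake also tend to have higher DCFBC uptake. A high rho does not show that DCFBC sees the NaF-positive sites, and a low rho does not show that it misses them.

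The protocol's own background makes discordance in bone worth counting. In the cited five-patient DCFBC study (2.2), 21 sites were concordant with conventional imaging, 5 of them in bone, and all 10 sites positive on conventional imaging but negative on DCFBC were in bone. That is 5 of 5 + 10 = 15 conventional-positive bone sites, or 33%. Most or all of the 10 may not be tumour, since they were judged indeterminate or traumatic. But one true bone metastasis was also reported as DCFBC-negative, and some DCFBC-only findings were put down to possible early bone metastases. At stake is whether Arm 3's paired scans yield an interpretable count of agreement and disagreement in both directions.

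**Working it through.** **1. The plan's own precision figure.** No sample size or precision is given for the NaF correlation. The only precision figure for Arm 3 is the expected 90% interval for mean concordance in 14.1, with mean 0.70, SD 0.43 and n = 20.

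- Formula: mean ± 1.645 × SD/√n.
- n = 20: 0.70 ± 1.645 × 0.43/√20 = 0.70 ± 0.158, giving (0.542, 0.858). The plan states (0.54, 0.86).
- Arm 1, n = 12: 0.70 ± 0.204, giving (0.496, 0.904). The plan states (0.50, 0.90).

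Both reproduce.

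**2. What rho can and cannot show.** Spearman's rho depends only on ranks. Multiplying every DCFBC value by one positive constant, or applying any strictly increasing transformation, leaves the ranks and so rho unchanged. The number of sites above a fixed background does change.

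The size of this effect is illustrated with 200,000 simulated NaF-positive lesions. The log DCFBC tumour-to-background ratio is μ + 0.4e, where e is standard normal with a set correlation with NaF uptake. A lesion is DCFBC-positive if the ratio exceeds 1, so the expected share is Φ(μ/0.4). The values of μ, the 0.4 and the correlations are assumptions, not estimates from this trial.

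| Spearman rho | μ = −0.8 | μ = 0 | μ = 0.8 |
|---|---|---|---|
| about 0.68 | 2% | 50% | 98% |
| about 0.29 | 2% | 50% | 98% |
| about 0.00 | 2% | 50% | 98% |

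As a check, Φ(−2) = 0.023, Φ(0) = 0.50 and Φ(2) = 0.977. The DCFBC-positive share varies across each row while rho is fixed, and is the same down each column while rho varies.

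**3. Precision of the correlation itself.** Section 14.2 does not say whether the unit is the lesion or the patient. With one value per patient and n = 20, an observed rho of 0.5 has standard error √((1 + 0.5²/2)/17) = 0.257 on Fisher's scale. The 95% interval is tanh(0.549 ± 1.96 × 0.257), or about 0.05 to 0.78.

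**4. Precision of a per-man agreement proportion.** This uses the formula of step 1 with the plan's two SDs (0.43 from 14.1, 0.30 from 14.3). The number of Arm 3 men with bone sites is not stated, so 10 and 15 are assumptions. Both SDs belong to comparisons with conventional imaging, and carrying them over to NaF is also an assumption.

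| Contributing men | 90% half-width, SD 0.43 | 90% half-width, SD 0.30 |
|---|---|---|
| 20 | 0.16 | 0.11 |
| 15 | 0.18 | 0.13 |
| 10 | 0.22 | 0.16 |

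**The case against.** **The correlation matches the objective.** Section 1.2 speaks of comparing uptake, and detection appears only in the description of NaF. This stands: 14.2 does not contradict its objective. The gap is against the detection role that 1.2 and 4.1 give NaF.

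**Site-level comparison may already be covered.** Section 2.3 lists NaF beside CT and bone scan, 4.5 says NaF may be done as standard of care, and 12.1.3 has NaF reported like other clinical studies. If conventional imaging in 14.1 includes NaF, the concordance there covers part of the question. This stands as an ambiguity. Section 1.2 lists standard-of-care imaging and NaF as separate objectives, which points the other way, and the plan should say which is meant.

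**Men with newly found bone lesions.** A reader might infer that 14.2 leaves out men without previously known bone metastases, in whom an early lesion would be new. The text does not support this. It refers to metastatic disease to bone, without requiring that it was known or present at baseline, so a man whose bone lesion first appears on a study scan can fall within it. What is true is that his inclusion is not stated.

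**No comparison planned beyond the correlation.** A reader might infer this too, but 4.1 promises a scan-by-scan comparison. It lacks a measure, so the correct statement is limited to methods in section 14 that name NaF.

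**NaF is an imperfect reference.** Section 2.1 says that such bone findings can be nonspecific or benign. This stands, and it limits what any added measure may be called.

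**Conclusion.** The point holds in limited form. The only method in section 14 that names NaF is a Spearman correlation of uptake, and it carries no information on how often the two tracers agree on bone sites. That follows from the definition of a rank statistic and does not depend on the simulation, which only shows how far the two quantities can separate (2% to 98% positive at the same rho).

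The documents do not support saying that the plan fails its stated objective, that it excludes men with new bone lesions, or that an added measure would give DCFBC's sensitivity. Low agreement could partly reflect benign NaF uptake.

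This is a secondary analysis in a pilot study. The primary result, sample size and stopping rules are unaffected. Label: cheap improvement. The precision figures rest on the plan's SDs carrying over to NaF and, below 20 men, on an assumed number with bone sites.

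**What to change.** In 14.2, for Arm 3 at each imaging session, report:

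- (a) among men with at least one NaF-positive bone site, the per-man proportion of those sites that are DCFBC-positive;
- (b) among men with at least one DCFBC-positive bone site, the per-man proportion of those sites that are NaF-positive.

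Average each over the contributing men with a patient-level bootstrap interval, and state how many men contribute. The restriction is needed because Arm 3 admits men with soft-tissue metastases only (3.1.5.3), for whom a proportion can have a zero denominator.

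Also state:

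- that bone sites first seen on the study scans are included;
- the bone-positivity rule for each tracer (14.3 defines negative uptake only for soft tissue and lymph nodes);
- how sites are matched between the two scans;
- that the results are agreement with NaF, not sensitivity;
- whether NaF counts as conventional imaging in 14.1.

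Keep the Spearman correlation as descriptive.

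The cost is one more secondary table and a few sentences of definitions, with no extra scan or patient. Site calls under the new rules will be needed, because 12.1.3 lists only SUV per region of interest. The intervals will be wide, as the working shows, and should be presented as such.

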14.3 Interim Futility Analysis and Early Stopping Rule

To avoid excessive expense and radiation exposure, if ^{18}F -DCFBC PET/CT is not successful in identifying lesions, we implement the following interim futility analysis and early stopping rule.

We plan to stop the protocol if the first 5 patients with soft tissue lesions greater than 1 cm have negative uptake (defined as tumor uptake less than adjacent background soft tissue, or blood pool for lymph nodes). Otherwise, a separate interim analysis for Arm 1 and Arm 3 will be carried out after 8 patients in each arm have been accrued. These will be independent interim analyses for each arm and only affect the given arm. If the mean PET-positive rate, defined as the average of patient-specific PET-positive rate among the positive sites identified by the conventional imaging, is less than 60%, the study would be declared futile, otherwise the study would proceed with accrual. Assuming the standard deviation of patient-specific PET-positive rate is 0.30, the probability of stopping for futility is 83% when the true PET-positive rate is 0.5 and 17% when the true PET-positive rate is 0.70. Since Arm 2 will by criteria not have lesions on conventional imaging, they are excluded from this interim analysis and early stopping rule.

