Cho et al followed up with initial clinical experience with ^{18}F DCFBC in metastatic prostate cancer patients.[15] Five patients with metastatic disease were injected with 370 MBq (10 mCi) of ^{18}F DCFBC and serial PET/CTs obtained for 2 hours after injection. Based on visual and quantitative assessment, the highest ratio of tumor activity to background was seen at the 2 hour scan. PET images were considered positive if focal radioactivity was above adjacent background tissue or blood pool for lymph nodes or bone. Lean body mass maximum standardized uptake values (SUV_{max}) were obtained for regions-of-interest (ROIs) for quantitative measurements. Focal abnormal PET uptake was seen in 32 metastatic lymph nodes and bone lesions with median SUV_{max} of 5.6 for lymph nodes, and 3.6 for bone. Conventional imaging was concordant with PET findings in 21 sites, 5 of them bone. Discordant positive PET findings were attributed to possible early bone metastases or subcentimeter lymph nodes. All 10 positive sites on conventional imaging that were negative on PET, were in bone and considered indeterminate for malignancy or due to trauma. One true metastatic bone lesion that was PET negative could have been related to antiandrogen therapy.

Metabolite analysis was also done in 2 patients with high performance liquid chromatography with essentially no metabolism or defluorination of ^{18}F DCFBC in plasma at approximately 1 and 2 hours after injection. Radioactivity remained almost entirely within the blood plasma.

Surprisingly, blood pool activity remained moderately persistent through imaging. Possible explanations include binding to a free form of PSMA circulating in the blood. They tested the inhibitory capacity of unlabeled DCFBC to prevent PSMA from hydrolyzing N-acetylated aspartyl-glutamate in normal human plasma and found 3nM was the 50% inhibitory concentration.

Dosimetry calculations showed a mean effective dose of 19.9 ± 1.34 uSv/MBq. The highest mean absorbed dose (uGy/MBq) was the urinary bladder wall (32.4) then the stomach wall

CC Protocol Number: 14-C-0140
 Abbreviated Title: DCFBC in prostate cancer
 Version date: 10/27/2015
 CIP #: 9622

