3 PATIENT SELECTION

3.1 Eligibility Criteria

- 3.1.1 Subject is ≥ 18 years old
- 3.1.2 Platelet count $> 50,000/\text{mm}^3$
- 3.1.3 Eastern Cooperative Oncology Group (ECOG) Performance score of 0 to 2.
- 3.1.4 Ability to provide informed consent. All subjects must sign an informed consent form indicating their understanding of the investigational nature and risks of the study before any protocol-related studies are performed.
- 3.1.5 Categories
 - 3.1.5.1 ARM 1 only
 - 3.1.5.1.1 For patients with presumed localized disease (any T, N0, M0), a multiparametric MRI (standard of care at the NIH Clinical Center) must be performed within 4 months of the ^{18}F -DCFBC injection with findings suggestive for prostate cancer and a prostate lesion at least 6mm or greater. Must have histopathologic confirmation of prostate cancer prior to ^{18}F -DCFBC imaging.
 - 3.1.5.2 ARM 2 only:
 - 3.1.5.2.1 For patients status post radiation therapy for prostate cancer, any PSA increase from post radiation therapy nadir

OR

- 3.1.5.2.2 For patients status post prostatectomy, a PSA ≥ 0.2 ng/ml
- 3.1.5.2.3 Nonspecific or no evidence for disease on standard imaging modality
- 3.1.5.3 ARM 3 only:
 - 3.1.5.3.1 Patients must have identifiable metastatic disease on at least 1 clinically indicated imaging modality. If only soft tissue metastasis, one lesion must measure at least 6mm or greater. Patients must have confirmation of prostate cancer prior to ^{18}F -DCFBC imaging.

Note: A patient who is eligible for one arm, subsequently may cross-over into a different arm.

CC Protocol Number: 14-C-0140
Abbreviated Title: DCFBC in prostate cancer
Version date: 10/27/2015
CIP #: 9622

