14 STATISTICAL CONSIDERATIONS

14.1 Primary Analysis

This is a single site three-arm pilot study, where prostate cancer patients are enrolled into different arms according to their disease types: localized (Arm 1), recurrent (Arm 2) or metastatic (Arm 3). The primary objective of this study is to assess the ability of ^{18}F -DCFBC to identify sites of localized, recurrent and metastatic prostate cancer. To achieve this goal, ^{18}F -DCFBC PET/CT and conventional imaging will be used to identify positive suspected sites, and the proportion of positive concordance will be used to assess the performance of ^{18}F -DCFBC. In a recent study (Cho et al., 2012), 32 positive suspected sites in five prostate cancer patients with metastasis were identified by ^{18}F -DCFBC PET/CT with 21 concordant on both ^{18}F -DCFBC PET/CT and conventional imaging. At the individual level, the number of positive suspected sites ranged from 2 to 12 with the patient-specific concordance rate ranging from 0 to 100%. The overall concordance rate which was the average of individual-specific estimates across patients equaled 64% with corresponding standard deviation equal to 43%. For the new study, assume that for patients in Arm 1 and Arm 3, the mean concordance rate is 70% with 43% standard deviation as observed in Cho et al. With 12 evaluable patients in Arm 1, the 90% expected confidence interval for the mean concordance rate is (0.50, 0.90). With 20 evaluable patients in Arm 3, the 90% expected confidence interval for the mean concordance rate is (0.54, 0.86). For patients in Arm 2 (recurrent disease), it is unlikely to identify suspected lesions by conventional imaging at the baseline. These patients will be followed according to the protocol.

Amendment E Addendum:

Sensitivity of ^{18}F -DCFBC uptake in prostate cancer patients in Arm 2 is evaluated by its ability in differentiating mean values of PSA between PET-CT positive and PET-CT negative patients. To this end, the current study with sample size 35 for Arm 2 is under-powered to detect a sizeable mean difference in PSA between the two groups. Based on the preliminary data of the study, log-transformed PSA is approximately normally distributed with standard deviation equal to 1.3. Assume 1:2 allocation of PET-CT negative vs. PET-CT positive

CC Protocol Number: 14-C-0140
Abbreviated Title: DCFBC in prostate cancer
Version date: 10/27/2015
CIP #: 9622

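### Do the 83% and 17% interim stopping probabilities in Section 14.3 need changing because they rest on an unsourced SD of 0.30?

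*Combined protocol and SAP*

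**What the plan says.** Section 14.3 sets two futility checks. This point concerns the second: "a separate interim analysis for Arm 1 and Arm 3 will be carried out after 8 patients in each arm have been accrued". The statistic is the mean over patients of each patient's share of conventional-imaging-positive sites that are also positive on PET. If that mean "is less than 60%, the study would be declared futile, otherwise the study would proceed with accrual". Performance is stated under one SD, introduced as an assumption: "Assuming the standard deviation of patient-specific PET-positive rate is 0.30, the probability of stopping for futility is 83" per cent when the true rate is 0.5, and it is 17% when the true rate is 0.70.

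Section 14.1 plans the precision of the primary estimate in the same two arms with a different value: "assume that for patients in Arm 1 and Arm 3, the mean concordance rate is 70% with 43% standard deviation". The 43% is the between-patient SD of the concordance rate in the earlier five-patient study, where patients had 2 to 12 suspected sites and their rates ran from 0 to 100%.

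**The concern.** Two SDs, 0.30 and 0.43, are applied to per-patient rates in the same arms within a page or two. Only the larger has a source, and only the smaller is used to describe the stopping rule. A reader could fairly suspect that the rule has been made to look better than it is.

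There is also a structural reason to ask. A patient's rate is a proportion over that patient's sites, so with few sites it is necessarily variable. One lesion is enough to enter Arm 1, where eligibility (Section 3.1) asks for "findings suggestive for prostate cancer and a prostate lesion at least 6mm or greater". If sites are few, an SD of 0.30 cannot be reached, and a poor tracer would be carried forward more often than the implied 17% (100% minus 83%). Section 14.3 says the rule is there to limit cost and radiation exposure, so its real stopping probability matters.

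**Working it through.** **Inputs.** From Section 14.3: n = 8 per arm, cut-off 0.60, SD 0.30, true rates 0.5 and 0.70. From Section 14.1: SD 0.43 from five patients, 2 to 12 suspected sites each. The number of conventional-positive sites per patient is not given, so several values are tried.

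**1. Reproduce the plan's figures.** For a mean of 8 patients, P(stop) = Φ((0.60 − p)·√8 / SD).
- p = 0.5: Φ(0.10 × 2.828 / 0.30) = Φ(0.943) = 82.7%.
- p = 0.70: Φ(−0.943) = 17.3%.

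These are the stated 83% and 17%.

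**2. Vary the SD, same formula.**

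| SD | Stop at 0.5 | Stop at 0.70 |
|---|---|---|
| 0.20 | 92.1% | 7.9% |
| 0.25 | 87.1% | 12.9% |
| 0.30 | 82.7% | 17.3% |
| 0.43 | 74.5% | 25.5% |
| largest possible | 71.4% (SD 0.50) | 26.8% (SD 0.458) |

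The largest possible SD of a rate with mean p is √(p(1 − p)), which is 0.50 at p = 0.5 and 0.458 at p = 0.70. By this formula, therefore, no SD can take the stopping probability at 0.5 below 71.4%.

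**3. Vary the number of sites.** With m independent sites in every patient, the SD is √(p(1 − p)/m). The arm stops if fewer than 60% of the 8m sites are PET-positive, so the probability is an exact binomial tail.

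| Sites per patient | SD at 0.5 / 0.70 | Stops if | Stop at 0.5 | Stop at 0.70 |
|---|---|---|---|---|
| 1 | 0.50 / 0.46 | ≤ 4 of 8 | 63.7% | 19.4% |
| 2 | 0.35 / 0.32 | ≤ 9 of 16 | 77.3% | 17.5% |
| 3 | 0.29 / 0.26 | ≤ 14 of 24 | 84.6% | 15.3% |
| 6 | 0.20 / 0.19 | ≤ 28 of 48 | 90.3% | 5.7% |

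The 63.7% needs exactly one site in all 8 patients. It is below 71.4% because the outcomes are coarse: 4 of 8 (50%) stops and 5 of 8 (62.5%) continues, with nothing between. From three independent sites upward the rule does better than the plan states.

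Sites within a patient are likely to be correlated, which raises the SD. With m sites and correlation ρ, SD² = p(1 − p)[ρ + (1 − ρ)/m]. At m = 6, an SD of 0.30 corresponds to ρ = 0.23 (p = 0.5) or 0.31 (p = 0.70). The plan's 0.30 therefore already leaves room for moderate clustering.

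**4. How much weight can 0.43 bear?**
- *Denominator.* Section 14.1's rate is taken over PET-positive sites (21 of 32 concordant). The interim rate is taken over conventional-positive sites. These are different proportions.
- *Precision.* With 4 degrees of freedom, a normal-theory 95% interval for the SD runs from √(4 × 0.43² / 11.14) = 0.26 to √(4 × 0.43² / 0.484) = 1.24. It contains 0.30. The upper end exceeds what a rate can have, which shows how little five patients say about an SD.
- *Could the earlier counts supply the right SD?* Section 2.2 reports that "All 10 positive sites on conventional imaging that were negative on PET, were in bone", and adds that they were thought indeterminate or traumatic. It is unclear whether such sites would count at the interim, and no per-patient counts are given. The SD of the interim rate cannot be derived from the documents.

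**The case for a change.** The strongest opposing case does not need 0.43 at all. With non-negative correlation within patients, the SD is at least √(p(1 − p)/m), so 0.30 is out of reach with one or two sites per patient. The plan gives no expected number of sites, and Arm 1 admits men with a single lesion. If Arm 1 patients mostly have one or two, the chance of continuing with a tracer at a true rate of 0.5 is 23% (two independent sites each) to 36% (one each), against an implied 17%. One sentence giving a source or a range would cost nothing.

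Much of this stands. The 0.30 has no stated source, the performance figures depend on it, and for an arm of single-lesion patients they would be too favourable. But an entry minimum is not an expected count, and the one-site case is unlikely to hold in Arm 3, given 2 to 12 suspected sites per patient in the earlier metastatic study. A range that shows only the unfavourable cases would mislead as much as a single figure does, because lower SDs and more sites give better performance than stated. What remains is a request for a source or a balanced sensitivity line, which is missing detail and not an error.

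**Conclusion.** No change to the plan is needed. The 83% and 17% are correct for the SD stated, and that SD is labelled as an assumption. The documents do not contradict it: the 0.43 in Section 14.1 measures a different rate in five patients, with an interval that includes 0.30.

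By the plan's own formula, SDs of 0.20 to 0.43 give stopping probabilities of 92% to 74% at a true rate of 0.5 and 8% to 26% at 0.70. The exact 64% / 19% is an extreme case, relevant mainly to Arm 1 and only if every patient has one site.

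The deciding point is that the SD is not part of the rule. An arm stops if the observed mean over 8 patients is below 60%, whatever the spread. The same data lead to the same decision under any assumed SD, and the sample size, primary analysis and later conclusions are untouched. The SD affects only the advance description of the rule, and a statistician reporting the interim can set the observed SD and site counts beside that description.

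This rests on the normal approximation for the SD table, on independent sites and equal site counts for the binomial table, and on the absence of per-patient data that would fix the true SD.
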